9.5 Complete of the study

9.5.1 Complete of the safety data collection

The participants who take the vaccination, and complete safety observation from day 0 to 28, and reported SAEs till the end of the study will be considered as complete of the safety data collection.

9.5.2 Complete of immunogenicity data collection

The participants who meet the inclusion and do not meet any exclusion criteria, take the vaccination, and complete the blood collection within day 28 post-vaccination will be considered as complete of the immunogenicity data collection.

9.6 Protocol violation and protocol deviation

9.6.1 Protocol violation (including but not limited to)

- No informed consent signed by the participant.
- The enrolled participant does not meet the all the inclusion criteria or meet one or more exclusion criteria.
- The investigator improperly asks the participant to withdraw from the study.
- The participant received incorrect intervention (i.e. vaccinated with other groups of vaccines mistakenly).
- The participant received a vaccine fail to meet the requirements.
- Any other reasons identified by the investigators and confirmed by the principal investigator.

For any protocol violation, the investigators should report to the principal investigator and sponsor in time, and the principal investigator should handle the protocol violation properly, collect all relevant information about the involved participants, particularly the safety associated data and follow-up to ensure the safety of the participants. The

principal investigator should also take proper measures to prevent the occurrence of similar protocol violation in the trial.

Investigators or monitors should report any protocol violation to principal investigator, coordinators and ethics committees as soon as possible after knowing the protocol violation by fax or e-mail.

9.6.2 Protocol deviation (including but not limited to)

- Beyond the visiting time window.
- Low compliance of participants, and the participants do not complete the blood sample collection.
- Serious adverse events do not report in time (SAE).
- Participants are treated with unallowed drugs (intramuscular, oral or intravenous corticosteroids for $\geq 2\text{mg/kg/days}$, continuous use for ≥ 14 days, or other immunosuppressants).
- The interval between vaccination with other vaccines is insufficient.
- Other reasons considered as protocol deviation by the principal investigator.

The protocol deviation should be recorded in detail. For the participants who exceeded the time window or had insufficient time interval of receiving other vaccines, the data of them can be included in the safety and immunogenicity analysis. For participants have other protocol deviation, the data of them can still be involved in the safety analysis, but can not be included in the immunogenicity analysis.

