	
express the specific S protein of SARS-CoV-2, which is prepared by amplification and purification. Preclinical studies suggest that both humoral and cellular immune responses play important roles in protective immunity. This is a phase I clinical trial to evaluate the safety, tolerability and immunogenicity of recombinant novel coronavirus vaccine (adenovirus type 5 vector) at 5×10^{10}vp, 1×10^{11}vp and 1.5×10^{11}vp in healthy adults aged between 18 and 60 years old.

Investigational vaccine
	
The recombinant novel coronavirus vaccine (adenovirus type 5 vector): Manufactures: Beijing Institute of Biotechnology and CanSino Biologics Inc. 0.5ml/ vial. Batch number: 202003001C. Valid until: 2022.02.28. Dosage: 5×10^{10}vp, 1×10^{11}vp and 1.5×10^{11}vp
 
Immunization: intramuscular injection at the lateral deltoid muscle of the upper arm on day 0.
 
Temperature for storage and transportation: at 2-8 °C

Trial design
	
Study design: a single-center, open-label, dose-increasing study.
 
Sample size: according to the "Technical guidelines for Vaccine Clinical Trials" issued by the China FDA, the sample size of each vaccine dose group is about 20-30 participants. In this study, 36 participants will be involved in the low-dose group, the middle-dose group and the high-dose group, respectively. A total of 108 participants will be recruited.
 
Study process: This study is performed in three steps: first, the low dose group (5×10^{10}vp); then, the middle dose group (1×10^{11}vp); at last, the high dose group (1.5×10^{11}vp), with 36 participants in each group. The trial will be carried out step by step from the low dose group to the high dose group, and the participants will be recruited sequentially. During the study, if any safety problems of the vaccine is noted, recruiting process should be stopped. The participants will be screened before involved in the study, and all the contents of the study will be completed through 9 visits. Study groups and dose increasing process are shown in the following table.

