10.7.1.1 Initial analysis

After the last participant complete the Visit 6 (28 days after vaccination), the research database has been entered, audited and locked, initial analysis will be done by the statistical party. The initial statistical analysis report shall first be reviewed by the DSMB and determined that the report shall be carried out in strict accordance with the initial statistical analysis plan before it can be submitted to the researcher and sponsor.

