10.7.3 Analyzed data sets selection

Data set for safety evaluation

All participants who received vaccination should be included in the safety evaluation.

Data that violate the scheme should not be excluded.

Data set for immunogenicity evaluation

Full analysis set (FAS) for immunogenicity analysis: FAS is based on ITT (intention to treat analysis) principle to determine the participants. All of the participants that meet the inclusion / exclusion criteria, receiving vaccination, and have at least one blood testing result after vaccination, were included in the FAS set for immunogenicity.

Per-protocol set (PPS): It is a subset of FAS. The participants in the data set were more compliant to the scheme, with no significant deviation or violation of protocol, all met the selection/exclusion criteria and completed vaccination within the vaccination time window according to the requirements of the scheme, and the participants who collected blood at day 0, day 7, day14, day 28 day, month 3 and month 6 month were included in the PPS set. This method of analysis does not include participants who violate the protocol, and confirmed as COVID-19 cases within 14 days after vaccination.

In this study, the FAS are the primary analysis set for immunogenicity evaluation, but the PPS will also be analyzed at the same time. Any difference of analysis results existed between PPS and FAS, will be discussed in the report.

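### Catch-all violations and deviations, left to the principal investigator's discretion with no criterion or cut-off, can remove immunogenicity data after the day-14 and day-28 results have been reported

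*Protocol*

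**What the plan says.** **Deviations (Protocol 9.6.2).** The list is expressly non-exhaustive and ends with "Other reasons considered as protocol deviation by the principal investigator". Data affected by a missed visit window or a short interval to another vaccine are kept in both analyses. With any other deviation the data may be used for safety "but can not be included in the immunogenicity analysis". No analysis set is named. The only procedural condition is "The protocol deviation should be recorded in detail".

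**Violations (Protocol 9.6.1).** The list includes "Any other reasons identified by the investigators and confirmed by the principal investigator".

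**Analysis sets (Protocol 10.7.3).** The FAS is the primary immunogenicity set. It requires eligibility, vaccination and at least one post-vaccination blood result, and it has no exclusion for deviations. The PPS removes significant deviations, without defining significant, and violations: "This method of analysis does not include participants who violate the protocol". It also requires blood samples through month 6.

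**Timing (Protocol 10.7.1.1 and 10.7.1.2).** The initial analysis follows the last day-28 visit and a database lock. The DSMB reviews the report "before it can be submitted to the researcher and sponsor". The final analysis, which includes humoral and cellular data, follows the last month-6 visit.

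**Masking (Protocol summary, Trial design).** "Study design: a single-center, open-label, dose-increasing study".

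**The concern.** An exclusion from an immunogenicity analysis is harmless only if it cannot depend on the response. Here the ground for exclusion is whatever the principal investigator considers a deviation, the consequence is mandatory, and nothing ties the decision to a date or to being unaware of the assay results. Dose is known throughout, and by the final analysis the researcher has the initial report.

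Membership of an analysed set could therefore follow the outcome, even without intent: a low responder's file may simply be looked at harder. GMT, fold increase and seroconversion would shift, and a difference between dose groups could appear or disappear. Immunogenicity is a secondary objective, but day-28 ELISA and neutralising antibody are named as the primary immunogenicity evaluations (10.5.1.3, 10.5.2.3), and groups are compared at P ≤ 0.05 (10.7.4).

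**Working it through.** **Step 1. Which sets does the discretion reach?**

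| Rule | PPS | FAS |
|---|---|---|
| 10.7.3 governs | Reached: violations and significant deviations are removed | Not reached: no exclusion for deviations |
| 9.6.2 governs | Reached | Reached: the rule covers the immunogenicity analysis without limit |

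The protocol does not say which section prevails. The PPS is affected either way; the FAS only in the second case.

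**Step 2. Can the decision come after results are known?**

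- Day-28 analysis: the database is locked first (10.7.1.1), and unlocking needs definite evidence and signatures (10.6.8). This protects in part. The lock is not tied to classifying deviations, and titres arrive as external data (10.6.9) with no statement that they are withheld from the principal investigator.
- Final analysis: visit 8 is scheduled 5 months after visit 6 (Table 8-3-1-1). The initial report is out by then, and 9.6 sets no cut-off. Because the PPS requires the month-6 sample, its final membership cannot be settled until after that report.

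**Step 3. How large could an effect be?** The protocol gives no SD, power or expected seroconversion rate. Its only sample-size figure is 36 per group, and 3 × 36 = 108 reproduces the stated total. The rest is illustration.

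Assume normal log10 titres with SD σ from 0.4 to 0.6, n = 36, and the k lowest removed from one group. With E(i) the expected i-th smallest of 36 standard normal values,

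GMT ratio = 10^(σ × S_k / (36 − k)), where S_k = −[E(1) + … + E(k)].

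Numerically, E(1) = −2.118, E(2) = −1.704, E(3) = −1.462.

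- k = 2: S = 3.822 and 3.822/34 = 0.1124. The ratio is 10^(0.4 × 0.1124) = 1.109 at σ = 0.4, 1.138 at σ = 0.5 and 1.168 at σ = 0.6.
- k = 3: S = 5.284 and 5.284/33 = 0.1601. The ratio is 1.159, 1.202 and 1.248.

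So the GMT rises by about 11% to 17% with two dropped and 16% to 25% with three. Simulation gives the same values.

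**Type I error.** Two groups with no true difference, the 2 lowest removed from one only, two-sided t-test at 0.05: simulated error is about 8.7%, against about 5% with none removed. This does not depend on σ.

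**Seroconversion**, with two non-converters removed: 27/36 = 75.0% becomes 27/34 = 79.4%; 34/36 = 94.4% becomes 34/34 = 100%. The starting counts are assumed.

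**The case against.** The case against has four parts.

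- **The FAS is primary and has no exclusion for deviations.** Under 10.7.3 a discretionary deviation cannot move the primary result, and FAS–PPS differences must be discussed in the report. This stands as far as 10.7.3 governs. A reader might infer that the primary analysis is exposed whichever set is used; the documents do not support that. They leave a conflict between 9.6.2 and 10.7.3.
- **There are safeguards.** They include the lock, DSMB review of adherence to the initial analysis plan, an audit trail in the data system (10.6), prompt reporting of violations (9.6.1) and a separate statistical party. These largely protect the day-28 analysis, and a later removal of day-14 or day-28 data could be seen by comparison with the initial report. They do not prevent an exclusion declared between the two analyses.
- **Open-label means that dose is known, not titre.** Correct. Nothing gives the principal investigator individual titres before the initial report, but nothing withholds them either.
- **The statistical analysis plan may set a pre-lock review of deviations.** It may, and its absence from the protocol would be no finding. But the open category and the mandatory exclusion are rules that the protocol itself states, and they need correcting there.

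A reader might also infer that low responders will be dropped, or that the reported GMT is biased upward. The text shows only that this is possible. The figures assume removal of exactly the lowest responders from one group, which is a worst case.

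**Conclusion.** The concern holds in limited form. Sections 9.6.1 and 9.6.2 fix a badly bounded exclusion rule: discretionary ground, no cut-off and, in 9.6.2, a mandatory consequence with no named set. Its reach is certain for the PPS and conditional for the FAS. The exposure lies mainly in the final analysis. The primary safety endpoint is untouched, because these participants stay in the safety analysis.

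The size is illustrative only: about 11% to 17% on the GMT for two of 36 removed, resting on an assumed log10 SD of 0.4 to 0.6 and on worst-case selection. The correction is worth making because it is cheap and also settles the conflict between 9.6.2 and 10.7.3.

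**What to change.** In section 9.6:

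1. State in 9.6.2 that exclusions based on deviations apply to the PPS only, in line with 10.7.3.
2. State that a discretionary violation or deviation (the open items in 9.6.1 and 9.6.2) excludes data only if it is listed with its reason and signed before that participant's immunogenicity results are released through the external-data transfer (10.6.9). Discretionary items declared later are recorded but remove no data.
3. State that objective grounds named in advance, such as no consent, ineligibility, wrong vaccine or the listed prohibited drugs, continue to apply whenever they are discovered. A blanket ban on exclusions after the initial report would go too far, because it would keep such participants in.

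The cost is a few sentences in 9.6 and one in the data-transfer agreement. No visit, procedure or safety report changes. The downside is that the deviation list must be signed before titres are released, which may delay the principal investigator's access to them.

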10 METHODS AND PROCEDURES

10.1 Participants screening

10.1.1 Screening before enrollment

Healthy people aged from 18 to 60 years were selected as the target population, the recruitment was promoted by the recruitment advertisement approved by the ethics committee, and the volunteers were selected before enrollment on the premise that they signed the informed consent approved by the ethics committee. Before they sign the informed consent, they will have enough time to think about it, and a withdrawn at any time during the trial is permitted.

Following operation will be performed during the selection:

- Demographic data.
- Physical examination, including general physical examination and laboratory examination.
- Medical history of disease.
- Meet all the inclusion criteria and do not meet any of the exclusion criteria.

10.1.2 Screening contents

10.1.2.1 Pregnancy test

Before vaccination, HCG detection will be performed on target women of childbearing age, those with negative test results can be enrolled.

10.1.2.2 HIV antibody screening

During the screening process, 3ml of coagulative venous blood of all participants will be collected for antibody screening, those with negative results can be enrolled.

10.1.2.3 Blood routine test

During the screening process, 2ml of anticoagulant venous blood will be collected from all participants for blood routine test, those with the tested indexes in the normal range, or determined by the doctor as not clinically significant could be enrolled.

10.1.2.4 Blood biochemical test

During the screening process, 3ml of procoagulant venous blood will be collected from all participants for blood biochemical test, those with the tested indexes in the normal range, or determined by the doctor as not clinically significant could be enrolled.

10.1.2.5 Antibody screening

Specific IgM and IgG antibodies against S and N in the serum of the participants will be tested by chemiluminescence assay, those who are positive for any of the antibodies will not be enrolled.

10.1.2.6 Nucleic acid of SARS-CoV-2 screening

Pharyngeal swabs or sputum and anal swabs are collected and detected by RT-PCR or /and NGS methods. Those who are positive for the nucleic acid of SARS-CoV-2 will not be enrolled.

10.1.2.7 Chest CT screening

All the participants will have a chest CT, and those who have COVID-19 imaging features will not be enrolled.

10.2 Enrollment

Eligible participants will be screened and assigned a study ID in order. A total of 108 participants will be allocated to the low, middle or high dose groups sequentially, with 36 participants per group.

10.3 Vaccine inoculation

10.3.1 Investigational vaccine

The investigational vaccine used in this study is a novel recombinant coronavirus vaccine (adenovirus type 5 vector) jointly developed by Beijing Institute of Biotechnology and CanSino Biologics Inc.

The investigational vaccine is a liquid formulation, using replication-defective human adenovirus type 5 as a vector, and express the specific S protein of the SARS-CoV-2.

The low, middle and high doses were 5×10^{10} vp (0.5ml), 1×10^{11} vp (1.0ml), and 1.5×10^{11} vp (1.5ml), and the quality is in line with the “recombinant new coronavirus vaccine manufacturing and verification regulations (draft)”. The investigational vaccine has got the certification from National Institutes for Food and Drug Control.

10.3.2 Administration

Low dose group (5×10^{10} vp/vial, 1 vial): take a vial of investigational vaccine, use a disposable syringe to extract 0.5ml vaccine and intramuscularly inject it into the middle of the lateral deltoid muscle of the participant's upper arm. The injection dose is 5×10^{10} vp for the participants in the low dose group.

Middle dose group (5×10^{10} vp/ vial, 2 vials): take 2 vials of investigational vaccine, use a disposable syringe to extract 1.0ml vaccine and intramuscularly inject it into the middle of the lateral deltoid muscle of the participant's upper arm. The injection dose is 1×10^{11} vp for the participants in the middle dose group.

High dose group (5×10^{10} vp/vials, 3 vials): take 3 vials of investigational vaccine, use two disposable syringes to extract 0.5ml and 1.0ml vaccine and intramuscularly inject

them into the middle of the lateral deltoid muscle of the participant's two upper arms, respectively. The injection dose is 1.5×10^{11} vp for the participants in the high dose group. Before injection, 75% alcohol is used for disinfection at the injection site and then intramuscular vaccination will be administered. Shaking the vaccine before use. No intravascular, intradermal or subcutaneous injection is allowed with the investigational vaccine.

In case any emergency situation may happen to the participants during the vaccination or during the 6-hour observation after vaccination, appropriate emergency medical equipment and doctors should be prepared.

10.3.3 Vaccine management

The sponsor should provide all the investigational vaccines, including the backup vaccines. The package of the investigational vaccines must comply with the requirements of clinical trials.

The sponsor is responsible for transporting the investigational vaccine to the clinical trial site, along with a transportation temperature record (in accordance with the cold chain temperature of the vaccine) and the inspection report (qualified). The vaccine management personnel of the research institution and the vaccine management personnel at the test site shall jointly check and sign with the sponsor.

Special area should be used to store and lock the test vaccine to get rid of unauthorized persons. Vaccine is forbidden to inject other ones except participants.

The cold storage should be equipped with a temperature recorder to monitor the temperature of the cold storage in real time. The cold storage administrator inspects the

cold storage every morning and afternoon and records the temperature of the cold storage to ensure the normal operation of the cold storage. If the cold storage temperature is found to exceed the cold chain preservation temperature of the vaccine, the cold chain temperature of the vaccine should be restored in time, and the test vaccine should be temporarily sealed and reported to the sponsor in writing in a timely manner. it must be approved in writing by the sponsor before it can continue to be used. Vaccines that do not meet the requirements should be sealed on the spot and continued use is strictly prohibited.

The investigational vaccine should be stored in a refrigerator or freezer and cold chain equipment is equipped with a thermometer with the vaccine administrator records temperature every 15 minutes.

Vaccine administrators release the investigational vaccine to the vaccination staff according to number of participants and vaccine. The left test vaccine packing should be recycled after inoculation and detailed records of test vaccine and recycling packaging are needed

After the completion of the vaccination day, the vaccine administrator will check the remaining investigational vaccines and the packaging of the vaccinated vaccines, and all of them will be recycled into the warehouse.

At the end of the study, the investigators will check all the remaining vaccine and package and deliver them back to sponsors.

At any time, the total number of vaccines, unused or damaged vaccines must be consistent with the applicants provided, otherwise, description is needed to be provided

by investigator.

10.3.4 Combined medication/vaccine

When the medical events happen during the study period, the participant are allowed to carry out the appropriate medical treatment, but the medical treatment should be recorded in time.

Other vaccination is not recommended except for emergency during the research period, such as rabies vaccine, tetanus vaccine, or other emergent vaccination need. Any vaccine used is required to be recorded during the study period.

10.4 Safety observation

10.4.1 Methods of safety observation

After vaccination, all participants are required to stay in the designated temporary lodgment for a safety observe of 14 days and then they are allowed to be back to their home for further safety observation since day 15 post-vaccination. The contents of safety observation during the study period are as follows:

(1) After vaccination, the participants will stay at the clinic for 6-hour observation and the temperature will be captured by both wireless remote continuous temperature measurement system and routine axillary thermometer.

(2) Within 14 days after vaccination, the participants are asked to complete the safety observation by themselves, and record the results on the "diary card". A designated doctor is responsible for visit the participants every day and instruct them to complete the diary card.

(3) From the day 15 to the day 28 after vaccination, the participants will be instructed

to record any adverse events on the "diary card" by themselves. On day 28, the investigators visited the participants, retrospectively investigated and verified the contents of the safety observation.

(4) During the whole study period (about 6 months after vaccination), the participants will be asked to report any serious adverse events following the vaccination.

